6.3.2 Visit 11/Last Titration Visit

Visit 11/Last Titration Visit is intended to confirm that the subject tolerates lixivaptan at the dose determined during the Titration Period and to collect additional data before entering the Maintenance Period. The procedures specified for Visit 11 may be performed at an earlier titration visit if the subject qualifies to enter the Maintenance Period at that time. The last titration visit may be in the office or conducted remotely by a HHC. If conducted remotely, telemedicine will be used for the Investigator to interact with the subject and confirm that the subject can continue into the Maintenance Period.

Subjects will either report to the clinic in the morning or interact with the HHC, if a remote visit is conducted, to undergo the assessments for the last visit of the Titration Period. Subjects should bring any remaining study drug into the clinic or provide to the HHC. Remind the subjects not to take their morning dose of lixivaptan on the morning of the visit. Dosing instructions will occur during the visit.

The following procedures will be performed:

- Collect and review concomitant medication information
- Review study drug compliance/reconciliation
- Assess study drug tolerability
- Check AEs and SAEs
- Assess clinically for liver dysfunction (symptoms, signs [if a clinic visit]) in accordance with the checklist and instructions in Appendix 4 ([Section 13.4](#)).
- Review lab results from prior visit
 - For subjects exhibiting an increase in ALT or AST during the Titration Period (>3 x baseline) or total bilirubin (>2 x ULN), follow the instructions in [Section 7.3.7](#)
- Measure body weight and counsel subject to increase fluid intake if weight decreases >3%
- Check vital signs (sitting blood pressure and heart rate)
- Collect urine to conduct a pregnancy test in WOCBP
- Collect blood for the following laboratory testing:
 - Complete chemistry panel
 - Liver chemistry panel
 - Hematology
- Collect a trough blood sample for measurement of lixivaptan. Note date and time of last dose from the previous day and the date and time of the sample on the requisition. The sample must be collected before the dose of lixivaptan is administered.
- The site will contact the IRT to complete subject's participation in the Titration Period, obtain new kit assignment, and enter the subject into the Maintenance Period and proceed as follows:
 - Dispense new kits. Have the subject take the first dose at home. Instruct the subject to take the appropriate dose twice a day approximately 10 hours apart, e.g., 8 AM and 6 PM.

- For remote visits, the site will contact the IRT sufficiently in advance of the scheduled visit day to obtain kit assignment and to allow sufficient time for study drug to be shipped to arrive at subject's home prior to the visit date.
- Schedule the subject for their next visit to occur in 4 weeks and remind the subject to take adequate fluids. Provide the subject with an appointment reminder card and any written instructions. Note that the next visit may be conducted remotely (if available).

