- For subjects exhibiting an increase in ALT or AST during the Titration Period ($>3 \times \text{ULN}$) or total bilirubin ($>2 \times \text{ULN}$), follow the instructions in [Section 7.3.7](#).
- Check AEs and SAEs
- Assess clinically for liver dysfunction (symptoms, signs [if a clinic visit]) in accordance with the checklist and instructions in Appendix 4 ([Section 13.4](#)).
- Check vital signs (sitting blood pressure and heart rate)
- Measure body weight and counsel subject to increase fluid intake if weight decreases $>3\%$
- Process an aliquot of first morning, fasting urine for specific gravity and assess if ≤ 1.005 has been reached (except if Level 4 or 4a)
- Send the remaining first morning, fasting urine for U_{osm} determination
- Collect a blood sample:
 - Liver Chemistry Panel
- Follow the flowchart in [Figure 4](#) to determine whether to increase the dose, decrease the dose, advance the subject to Visit 11 procedures to initiate the Maintenance Period, or discontinue the subject. For remote visits, the HHC will call the Investigator to receive direction on this decision. The Investigator may want to utilize telemedicine to interact with the subject.
 - Based on the decision made from the flowchart, contact the IRT to receive the kit assignment for the next period of time
 - Dispense study drug and instruct subject how many capsules to take based on the dose level guide in [Table 4](#)
 - For remote visits, the site will contact the IRT sufficiently in advance of the scheduled visit day to obtain kit assignment and to allow sufficient time for study drug to be shipped to arrive at subject's home prior to the visit date.
- At each visit, remind the subject to take adequate fluids, provide a urine collection container, and instruct the subject to collect a first morning, fasting (8 hours except for water) urine specimen on the morning of their next visit, which they will bring with them (if a clinic visit) or provide to the HHC if a remote visit is conducted.
- Provide the subject with an appointment reminder card and any written instructions.

Figure 4. Titration Flowchart

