6.4 Maintenance Period

The Maintenance Period will last 52 weeks (Visit 12 to Visit 24). If available, the following visits may be done remotely: Visits 12, 13, 14 (with telemedicine), 15, 16, 18, 19, 20 (with telemedicine), 21, 22, and 23. Note that telemedicine may be added to any other visit if the Investigator judges that additional interaction or information is needed to assess the subject's status.

6.4.1 Visits 12 to 23

Visits 12 to 23 will occur every 4 weeks \pm 3 days. For visits not done remotely, subjects will report to the clinic in the morning or afternoon on visit days. Subjects should bring any remaining study drug into the clinic or provide to the HHC.

The following procedures will be performed at each visit unless otherwise noted:

- Check vital signs (sitting blood pressure and heart rate)
- Review lab results from prior visit
 - For subjects exhibiting an increase in ALT or AST during the Maintenance Period (>3 x ULN) or total bilirubin (>2 x ULN), follow the instructions in [Section 7.3.7](#).
- Check AEs and SAEs and inquire about tolerability of the study drug
- Assess clinically for liver dysfunction (symptoms, signs [if a clinic visit]) in accordance with the checklist and instructions in Appendix 4 ([Section 13.4](#))
- Review study drug compliance/ reconciliation
- Collect and review concomitant medication information
- Perform a brief physical exam (Visit 17)
- Perform a 12-lead ECG (Visit 17)
- Collect urine to conduct a pregnancy test in WOCBP (Visits 14, 17, and 20 only).
- Collect a blood sample for the following laboratory testing:
 - Complete Chemistry Panel (Visits 14, 17, and 20 only)
 - Liver Chemistry Panel (all visits)
 - Hematology (Visit 17)
- Collect a plasma sample for trough measurement of lixivaptan *if* ALT > 3 x ULN and/or total bilirubin > 2 x ULN. Note date and time of last dose from the previous day and the date and time of the sample on the requisition form.

- At Visit 23, provide subject with a urine collection container and written instructions to produce a first morning, fasting (8 hours except for water) urine specimen to be brought in at Visit 24 for specific gravity and U_{osm} determination.
- The site will contact the IRT at each visit to obtain kit number assignment and complete the visit. Dispense assigned kits to subject for the next 4 weeks. Instruct the subject to take the appropriate dose twice a day approximately 10 hours apart, e.g., 8 AM and 6 PM.

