6.4.2 Visit 24/Early Termination

Visit 24 will occur at Week 52 ± 3 days.

Subjects will report to the clinic in the morning to undergo last Maintenance Visit assessments. These procedures will also be conducted on subjects that terminate the study early ([Section 6.5.4](#)).

Subjects should bring in any remaining study drug with them.

The following procedures will be performed:

- Collect and review concomitant medication information
- Review study drug compliance/reconciliation and collect all remaining study drug
- Review lab results from prior visit
 - For subjects exhibiting an increase in ALT or AST during the Maintenance Period ($>3 \times \text{ULN}$) or total bilirubin ($>2 \times \text{ULN}$), follow the instructions in [Section 7.3.7](#).
- Check AEs and SAEs
- Assess clinically for liver dysfunction (symptoms, signs) in accordance with the checklist and instructions in Appendix 4 ([Section 13.4](#)).
- Perform a full physical examination
- Measure body weight
- Check vital signs (sitting blood pressure and heart rate)
- Perform a 12-lead ECG
- Process an aliquot of first morning, fasting urine for specific gravity
- Send the remaining first morning, fasting for U_{osm} determination
- Collect urine for urinalysis
- Collect urine sample for a urine pregnancy test in WOCBP
- Collect blood for the following laboratory testing:
 - Complete chemistry panel

- Liver chemistry panel
- Hematology
- Collect a plasma sample for trough measurement of lixivaptan *if* ALT > 3 x ULN and/or total bilirubin > 2 x ULN. Note date and time of last dose from the previous day and the date and time of the sample on the requisition form.
- Contact the IRT to complete the visit.
- Schedule the subject to return to the clinic for the first follow-up visit (Visit 25) or schedule as a remote visit if available.

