6.5 Follow-up Period

The Follow-up Period will last 28 days and include 3 visits (Visit 25, Visit 26, and Visit 27). If available, Visits 25 and 26 may be done remotely by a HHC (with telemedicine if necessary).

6.5.1 Visit 25

Visit 25 will occur no earlier than 8 (+ 3) days after Visit 24. The following procedures will be performed at Visit 25:

- Check AEs and SAEs
- Review lab results from prior visit
 - For subjects exhibiting an increase in ALT or AST (>3 x ULN) or total bilirubin (>2 x ULN) at the prior visit, follow the instructions in [Section 7.3.7](#).
- Assess clinically for liver dysfunction (symptoms, signs [if a clinic visit]) in accordance with the checklist and instructions in Appendix 4 ([Section 13.4](#)).
- Collect and review concomitant medication information
- Collect a blood sample:
 - Serum creatinine
- Schedule the subject to return to the clinic for V26, in 7-14±3 days or confirm if it will be done remotely
- The site will contact the IRT to complete the visit

6.5.2 Visit 26

Visit 26 will occur 7-14±3 days after Visit 25. The following procedures will be performed at Visit 26:

- Check AEs and SAEs
- Collect and review concomitant medication information
- Collect a blood sample:
 - Serum creatinine
- Schedule the subject to return to the clinic for V27, 28±3 days after V24 (last dose of study drug) and provide a urine collection container and instructions for first morning, fasting (8 hours except for water) urine specific gravity and U_{osm} determination

- The site will contact the IRT to complete the visit

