7.3.7.1 Requirements for Additional Liver Chemistry Testing

To determine when repeat liver chemistry testing is necessary, follow the instructions in Table 7:

Table 7 Additional Liver Chemistry Testing and Other Testing

Subjects with Liver Chemistry Values Exceeding Eligibility Requirements at Screening or Baseline	Subjects with Eligible Liver Chemistry Values at Screening or Baseline

Subjects with transaminase (ALT/AST) or total bilirubin values above the values in the exclusion criteria ($>1.5 \times \text{ULN}$ and $>1.0 \times \text{ULN}$, respectively) during the Screening or Baseline Periods will not proceed further in the study. Any required follow up should be part of routine clinical care. However, if evaluation indicates a reversible cause of liver disease, such subjects may be re-screened in consultation with the medical monitor and sponsor when such liver chemistry test results return to values allowing entry into the study.
	
Any transaminase value $>3 \times \text{ULN}$ or total bilirubin $>2 \times \text{ULN}$ during the Titration or Maintenance Periods requires immediate retesting within 48 hours. Local laboratory testing is acceptable with collection of a concurrent central laboratory sample for confirmation whenever possible. During the time that values remain elevated, testing should be done at least weekly for the first month, gradually returning to monthly as indicated by the results. Individual cases that either resolve quicker or slower should be discussed with the medical monitor and sponsor. The medical monitor will discuss with the Investigator any additional laboratory testing or imaging depending on the case circumstances. Examples of such testing are shown in Appendix 3 (Section 13.3).

7.3.7.2 Changes in Study Drug Dosing if Liver Chemistry Test Abnormalities Occur During the Titration or Maintenance Periods

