After the Investigator consults with the medical monitor and sponsor, temporary reduction in dose or interruption of study drug administration must be instituted if liver transaminase levels $>3 \times \text{ULN}$ or total bilirubin levels $>2 \times \text{ULN}$ are observed during the Titration or Maintenance Periods. All elevations meeting these thresholds will be assessed the HERC. In the case of study drug interruption, re-starting study drug should be encouraged (see [exception](#) below) after discussion with the medical monitor and sponsor, when liver chemistry tests have normalized or stabilized, and in conjunction with a plan for increased frequency of liver chemistry test monitoring.

In the presence of such liver chemistry test abnormalities, additional clinical testing (examples listed in Appendix 3 ([Section 13.3](#))) may be recommended by the medical monitor and sponsor and those results reported according to local guidelines.

Treatment with study drug cannot be resumed in subjects when:

- transaminase levels $>8 \times \text{ULN}$ at any time,
- transaminase levels $>5 \times \text{ULN}$ for more than 2 weeks, or
- concurrent elevations of transaminase levels $>3 \times \text{ULN}$ **and** total bilirubin $>2 \times \text{ULN}$

except under these circumstances:

Subjects with these levels of abnormality may be re-challenged with study drug if abnormalities were adjudicated as having a $\leq 50\%$ likelihood of being related to study drug (per DILI Network [DILIN] probability criteria, modified, [Section 13.2](#) (Fontana RJ 2009)¹⁸ by the HERC, and the Investigator, medical monitor, and sponsor agree to an intensive monitoring plan to mitigate risk. The subject must also be willing to comply with these monitoring measures, be informed of the potential risks, and consent to study drug re-challenge.

Liver chemistry test increases of a lesser extent should be discussed with the medical monitor. They may be related to the underlying variability of such tests in ADPKD patients. Generally, dosing should continue, but the frequency of laboratory testing should increase, particularly during the Maintenance Period. Slowing of titration may also be considered if the abnormalities occur during the Titration Period.

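### Protocol Section 6.3.2 triggers the liver-abnormality procedures at ALT or AST above 3 x baseline, while the other visits and Section 7.3.7 itself use 3 x ULN

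*Protocol*

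**What the plan says.** Section 6.3.2 of the protocol lists the Visit 11/Last Titration procedures. One of them is to look at the previous visit's laboratory results and go to Section 7.3.7 for an "increase in ALT or AST during the Titration Period (>3 x baseline) or total bilirubin (>2 x ULN". The ALT/AST limit there is relative to baseline; the bilirubin limit is relative to ULN.

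The same step appears in the lists for other visits:

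- Section 6.3.1 (Visits 6 to 10) opens "For subjects exhibiting an increase in ALT or AST during the Titration Period" and sets the limit at 3 x ULN.
- Section 6.4.1 (Visits 12 to 23) refers to an "increase in ALT or AST during the Maintenance Period (>3 x ULN) or total bilirubin (>2 x ULN".
- Section 6.4.2 (Visit 24/Early Termination) begins "For subjects exhibiting an increase in ALT or AST during the Maintenance Period" and again sets 3 x ULN.
- Section 6.5.1 (Visit 25) reads "For subjects exhibiting an increase in ALT or AST (>3 x ULN) or total bilirubin (>2 x ULN) at the prior visit".

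Section 7.3.7, to which all of these point, works in ULN units. In Table 7 (Section 7.3.7.1) a transaminase above 3 x ULN "during the Titration or Maintenance Periods requires immediate retesting within 48 hours". Section 7.3.7.2 says that "temporary reduction in dose or interruption of study drug administration must be instituted if liver transaminase levels" pass the same 3 x ULN limit, and sends every such elevation to the HERC. Section 7.3.7.3 uses 3 x ULN for AESI reporting.

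After the Visit 11 procedures the site is told: "Schedule the subject for their next visit to occur in 4 weeks".

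**The concern.** One visit out of the whole treatment schedule uses a different reference for ALT and AST, and the documents do not say why. The protocol does use baseline-relative limits elsewhere, but for other purposes: inclusion criterion 7b describes the subject's history on tolvaptan, and Section 8.4.3 has a descriptive endpoint of ALT or AST above 2 x baseline. Neither explains the Visit 11 wording.

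This is operative text in a trial whose primary objective is hepatic safety. Every subject entering Maintenance goes through the Visit 11 procedures, which may be carried out remotely by a home healthcare clinician with telemedicine, and scheduled liver testing then drops from weekly to every 4 weeks. A site working from the visit list would apply an action level that differs from the section it is sent to. Section 6.3.2 also does not say which value is the baseline. Liver panels are drawn at Visits 3, 4 and 5, and the rule that baseline is the last value before first dose appears only in the statistical text (Protocol Section 8.4.5, SAP Section 7.1).

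**Working it through.** There is no planned figure to reproduce. The check is a comparison of the text, followed by simple arithmetic.

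**Step 1: the thresholds side by side.**

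| Protocol section | Applies to | ALT/AST | Total bilirubin |
|---|---|---|---|
| 6.3.1 | Visits 6 to 10 | >3 x ULN | >2 x ULN |
| **6.3.2** | **Visit 11/Last Titration** | **>3 x baseline** | **>2 x ULN** |
| 6.4.1 | Visits 12 to 23 | >3 x ULN | >2 x ULN |
| 6.4.2 | Visit 24/ET | >3 x ULN | >2 x ULN |
| 6.5.1 | Visit 25 | >3 x ULN | >2 x ULN |
| 7.3.7.1, Table 7 | Retest, Titration and Maintenance | >3 x ULN | >2 x ULN |
| 7.3.7.2 | Dose action and HERC review, Titration and Maintenance | >3 x ULN | >2 x ULN |
| 7.3.7.3 | AESI report | >3 x ULN | >2 x ULN |

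Only one cell differs. The primary endpoint in Section 2.2.1 also uses ALT >3 x ULN.

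**Step 2: convert the Visit 11 trigger to ULN units.** Let b be the subject's baseline divided by ULN. The Visit 11 trigger is T = 3 x b, and its distance from the Section 7.3.7 level is D = 3b - 3. Exclusion 17 rules out ALT or AST above 1.5 x ULN at Screening/Baseline, so b is at most 1.5. The documents give no baseline distribution, so the other values of b are assumed for illustration.

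| b (x ULN) | T = 3b (x ULN) | D = 3b - 3 (x ULN) |
|---|---|---|
| 0.5 (assumed) | 1.5 | -1.5 |
| 0.8 (assumed) | 2.4 | -0.6 |
| 1.0 | 3.0 | 0 |
| 1.2 (assumed) | 3.6 | +0.6 |
| 1.5 (exclusion 17 limit) | 4.5 | +1.5 |

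Setting 3b = 3 gives b = 1.0, the only baseline at which the two rules agree. Above it, the Visit 11 step stays silent for values between 3.0 and 3b x ULN. Below it, the step refers values that have not reached 3 x ULN.

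**Step 3: can both rules meet the same result?** Yes. Section 6.3.2 allows the Visit 11 procedures to be done at an earlier titration visit. In Table 5, Levels 2, 3, 3a and 4 finish in weeks 3 to 5, corresponding to Visits 8 to 10; only the Level 4a paths run to week 6. If the site works through both lists at such a visit, the same prior-visit result is judged twice. With an assumed b of 1.2 and a prior ALT of 3.4 x ULN, Section 6.3.1 refers the subject (3.4 > 3.0) and Section 6.3.2 does not (3.4 < 3.6).

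**The case against.** The best defence is that the Visit 11 step is a pointer and does not set the rule. Section 7.3.7 binds by itself for any transaminase above 3 x ULN in Titration or Maintenance. The result under review is about a week old, so a value between 3.0 and 4.5 x ULN should normally have led to retesting and dose action before Visit 11. Visit 11 also draws its own liver panel, which Section 7.3.7 governs and which Visit 12 reviews against 3 x ULN. This stands, and it is why no safeguard is lost.

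Low baselines err on the cautious side. Section 7.3.7.2 has a paragraph on smaller rises: discuss with the medical monitor, generally keep dosing, test more often. A subject referred early therefore finds guidance there. This also stands.

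The late-firing case is narrow. It needs a baseline between 1.0 and 1.5 x ULN, a value in the band just described, and a site that has missed Section 7.3.7. Exclusion 7 refers to a previously raised ALT having returned to 1 x ULN or lower for at least 3 months, which makes the case less common for ALT; it does not mention AST.

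Sites that run the Section 6.3.1 list at the same visit would meet the correct limit too. That does not remove the conflict, since it means two limits can govern one result. Finally, SAP Section 9 reports early termination with only 6 participants in Maintenance, so few subjects could have been affected. None of these points supplies a reason for the baseline reference.

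**Conclusion.** The concern holds. Section 6.3.2 states a decision threshold that conflicts with the parallel steps at other visits and with the section it refers to, and the documents offer no rationale. The discrepancy runs up to 1.5 x ULN too late at the highest permitted baseline (4.5 against 3.0 x ULN), and in the cautious direction for baselines below 1.0 x ULN. The upper figure rests on exclusion 17. How many subjects fall on either side cannot be said, because no baseline ALT or AST distribution is given.

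The consequence is a contradictory instruction at the move to 4-weekly testing. It is not demonstrated harm, and the endpoint definitions and analyses are unaffected. It should be corrected.

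**What to change.** In Section 6.3.2, change the ALT/AST limit from 3 x baseline to 3 x ULN, to agree with Sections 6.3.1, 6.4.1, 6.4.2, 6.5.1 and 7.3.7, and notify sites. The trigger is then 3.0 x ULN for every subject at each of these visits, and no definition of baseline is needed for this step.

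The edit is one word, with no new data and no change to any analysis. Under Section 11.2.1 a protocol amendment needs IRB/EC approval before it is implemented, so the administrative cost is somewhat more than a notice. Given the early termination, the practical benefit for this trial's sites is now small. Section 1.8 says the same titration scheme will be used in PA-ADPKD-301. That protocol is not among the documents here, and it would be sensible to check it for the same wording.

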6.4 Maintenance Period

The Maintenance Period will last 52 weeks (Visit 12 to Visit 24). If available, the following visits may be done remotely: Visits 12, 13, 14 (with telemedicine), 15, 16, 18, 19, 20 (with telemedicine), 21, 22, and 23. Note that telemedicine may be added to any other visit if the Investigator judges that additional interaction or information is needed to assess the subject's status.

6.4.1 Visits 12 to 23

Visits 12 to 23 will occur every 4 weeks \pm 3 days. For visits not done remotely, subjects will report to the clinic in the morning or afternoon on visit days. Subjects should bring any remaining study drug into the clinic or provide to the HHC.

The following procedures will be performed at each visit unless otherwise noted:

- Check vital signs (sitting blood pressure and heart rate)
- Review lab results from prior visit
 - For subjects exhibiting an increase in ALT or AST during the Maintenance Period (>3 x ULN) or total bilirubin (>2 x ULN), follow the instructions in [Section 7.3.7](#).
- Check AEs and SAEs and inquire about tolerability of the study drug
- Assess clinically for liver dysfunction (symptoms, signs [if a clinic visit]) in accordance with the checklist and instructions in Appendix 4 ([Section 13.4](#))
- Review study drug compliance/ reconciliation
- Collect and review concomitant medication information
- Perform a brief physical exam (Visit 17)
- Perform a 12-lead ECG (Visit 17)
- Collect urine to conduct a pregnancy test in WOCBP (Visits 14, 17, and 20 only).
- Collect a blood sample for the following laboratory testing:
 - Complete Chemistry Panel (Visits 14, 17, and 20 only)
 - Liver Chemistry Panel (all visits)
 - Hematology (Visit 17)
- Collect a plasma sample for trough measurement of lixivaptan *if* ALT > 3 x ULN and/or total bilirubin > 2 x ULN. Note date and time of last dose from the previous day and the date and time of the sample on the requisition form.

- At Visit 23, provide subject with a urine collection container and written instructions to produce a first morning, fasting (8 hours except for water) urine specimen to be brought in at Visit 24 for specific gravity and U_{osm} determination.
- The site will contact the IRT at each visit to obtain kit number assignment and complete the visit. Dispense assigned kits to subject for the next 4 weeks. Instruct the subject to take the appropriate dose twice a day approximately 10 hours apart, e.g., 8 AM and 6 PM.
- For remote visits, the site must contact the IRT sufficiently in advance of the scheduled visit day to obtain kit assignment and to allow sufficient time for drug to be shipped to arrive at subject's home prior to the visit date.
- Schedule the subject to return for their next visit or confirm if visit will be done remotely. The visit is to occur in 4 weeks. Provide the subject with an appointment reminder card and any written instructions.

